8 ENROLLMENT, TREATMENT ASSIGNMENT AND BLINDING

8.1 Method of Assigning Subjects to Treatment Groups

Up to 60 eligible patients will be randomly assigned to NORFLO[®] ORO or placebo treatment groups in a 1:1 ratio using a stratified randomization blocks scheme. The patient randomization list will be generated by Latis S.r.l., using the procedure PROC PLAN of SAS 9.4 for Windows (SAS Institute Inc., Cary, NC, USA).

8.2 **Blinding**

Due to the objectives of the study, the investigators, research staff, or patients will not know the treatment identity (test or control). The following study procedures will be in place to ensure double-blind administration of study treatments:

• Access to the randomization code will be strictly controlled.

Packaging and labeling of test and control treatments will be identical to maintain the blind.

The study blind will be broken on completion of the clinical study and after the study database has been locked.

During the study, the blind may be broken **only** in emergencies when knowledge of the patient's treatment group is necessary for further patient management.

The Principal investigator will receive a study treatment identification key in the form of sealed envelopes containing the kit number and the corresponding treatment.

The envelope can be opened only in case of an emergency presenting the need to disclose the identification of the study treatment assigned to the patient, for the purpose of establishing the appropriate therapy. Once the code is broken for a patient, this patient shall be withdrawn from the study, with the completion of the final study evaluation, indicating the specific reason of the patient withdrawal.

The Study Monitor must be notified immediately by the investigator of any emergency unblinding; the date and time, along with the reason for the unblinding, will be noted. Treatment codes will not be freely available to the investigator or personnel monitoring the study until after the study completion and database lock.

8.3 **Formulation of Test and Control Products**

8.3.1 Formulation of Test Product

NORFLO[®] ORO is a new formulation of Eye Pharma S.p.A., for oral administration. NORFLO[®] ORO is a yellow-colored solution that requires no reconstitution. See **Table 2** for the formulation of NORFLO[®] ORO.

	NORFLO [®] ORO	g/ST	Placebo	g/Kg
Active Ingredient,	Turmeric lecithin	0.500 g		
mg/mL	Turmeric - phosphatidylserin	ne 0.100 g		
Other ingredient,				
mg/mL	Erythritol	0.2891 g	Erythritol	165.67 g
	Silicon Dioxide	0.0175 g	Silicon Dioxide	4.53 g
	Polysorbate 20 (Tween 20)	0.0174 g	Polysorbate 20 (Twe	en 20) 9.99 g
	Isomalt	0.19 ² g	Isomalt	533.30 g

 Table 2 - Formulation and Measured pH of NORFLO® ORO and Placebo

Guar Gum	0.300 g	Guar Gum	171.92 g
Orange flavor	0.100 g	Orange flavor	57.31 g
Stevia	0.050 g	Stevia	8.60 g
Lemon flavor	0.100 g	Lemon flavor	28.65 g
Citric acid	0.008 g	Citric acid	4.58 g
Sucro ester E473	0.006 g	Sucro ester E473	0.006 g
		Sunset yellow (E110)	12 g

8.3.2 Formulation of Control Product

A placebo will be provided by Eye Pharma in a pack containing 30 single foil pouches ready for administration. The placebo composition is reported in Table 2.

8.3.3 Packaging and Labeling

Packaging: study product and placebo will be supplied in cartons containing 30 single foil pouches that are enough for a month-long treatment.

The study products will be delivered to the subjects based on the interval period between visits as indicated below:

Visit 1 (baseline, t₀): each patient receives 13 kits containing 30 single foil pouches

Visit 2 (t₁, 6 months): each patient receives 18 kits containing 30 single foil pouches.

Labeling: Each carton (kit) of study products will be labeled with the protocol number, a

treatment number, production lot, expiration date, the name of the sponsor, and directions for patient use and storage.

8.4 **Supply of Study Products at the Site**

Eye Pharma (or designee) will ship the Study Products to the investigational sites after sites activation (i.e. all required regulatory documentation has been received by Eye Pharma and a contract has been executed).

8.4.1 Dosage/Dosage Regimen

Study products will be administered as follows.

Two single foil pouches per day, each with main meals, with an estimated interval of about 8 hours between doses. A minimum interval of 4 hours between doses should be maintained.

The treatment will last for a period of 12 months.

Table 3 - Dosage	Regimen
------------------	---------

	Dosage regimen/ Each center	Administration	Minimum interval between doses	Duration
NORFLO [®] ORO	3.49 gr (2 single foil pouches of 1.7450 g) per day	Each single pouch (1.7450 g) at main meal in a glass of water	4 hr	12 months
PLACEBO	3.49 gr (2 single foil pouches of 1.7450 g) per day	Each single pouch (1.7450 g) at main meal in a glass of water	4 hr	12 months

8.4.2 **Dispensing**

Investigator (or designee) delivers the study product to the patient at each visit.

8.5 **Supply of Study Product at the Site**

8.5.1 Storage

Study products should be stored by the study site at controlled room temperature, 15 to 30°C (59 to 86°F). If the temperature of the study drug storage in the clinic/pharmacy exceeds or falls below this range, this should be reported to Eye Pharma (or designee) and captured as a deviation. Subjects will be instructed to store the medication in original packaging (foil pouch and protected from light) at room temperature.

8.6 Study Product Accountability

An accurate and current accounting of the dispensing and return of study product for each subject will be maintained on an ongoing basis by a member of the study site staff. The number of study product foil pouches dispensed and returned by the subject will be recorded on the appropriate form. The study monitor will verify these documents throughout the course of the study.

8.7 Measures of Treatment Compliance

Subjects will be asked to keep a patient diary noting the day and date they take the study product and any adverse events they experience. Subjects will be asked to bring their patient diary to each study visit along with all used and unused study product containers.

Due to non-compliance with study procedures, the investigator can withdraw subjects from study participation. The investigator will communicate promptly to Eye Pharma the patient withdrawal from the study.

9 STUDY PROCEDURES AND GUIDELINES

A Schedule of Events representing the required testing procedures to be performed for the duration of the study is diagrammed in APPENDIX 1. Data sheets on diagnostic ophthalmologic exams to be carried out during the study are shown in APPENDIX 2.

Prior to conducting any study-related activities, written informed consent must be signed and dated by the subject or subject's legal representative.

9.1 Clinical Assessments

9.1.1 **Demographics**

Patient demographic and baseline characteristic data to be collected on all patients includes: date and place of birth, place of living, sex, race, and ethnicity (where legally possible), work typology.

9.1.2 Concomitant Medications

All concomitant medications will be registered at baseline visit and their changes, if any, will be documented at each following visit. Dose, route, unit frequency of administration, and indication for administration and dates of medication will be captured.

9.1.3 Medical History

Relevant medical history, including history of current disease and information regarding underlying diseases, with special attention to ocular diseases and uveitis, will be recorded at baseline visit (t_0).

9.1.4 Physical Examination

A physical examination will be performed by the investigator at baseline visit (t₀). Qualified staff may complete the abbreviated physical exam at all other visits. New abnormal physical exam findings during the study must be documented as adverse event and will be followed by a physician or other qualified staff at the next scheduled visit.

A rheumatologic evaluation will be done at screening in order to assess if the whether the disease also has a systemic involvement (ankylosing spondylitis) or not.

9.1.5 Urine dipstick specific pregnancy test

Urine dipstick specific pregnancy test will be performed at the site at baseline and at each following visit. The study products cannot be administered if the pregnancy test results positive or doubtful.

9.1.6 Adverse Events

Information regarding occurrence of adverse events will be captured throughout the study. Duration (start and stop dates and times), severity/grade, outcome, treatment and relation to study product will be recorded on the case report form (CRF).

9.1.7 Vital Signs

Systolic and diastolic blood pressure and heart rate will be measured at baseline and at each following visit.

9.2 **Ophthalmological exams guide**

Both eyes will be evaluated at each visit.

9.2.1 BCVA

One goal of a complete eye examination is to determine the best corrected visual acuity (BCVA). Normal visual acuity is generally accepted as 20/20, although many people can see 20/15, and a few can see 20/10. If the eye cannot see 20/20 with a glasses or contact lens correction, then a refraction is required to determine the BCVA.

The visual acuity testing protocols recommended are:

• Distance acuity with correction (CC) if the patient needs glasses or contact lenses for the best distance vision. The exception is visual acuity testing after cataract or refractive surgery, as these procedures will likely change the refractive status of the eye.

• Distance acuity without correction (SC) if the patient wears no glasses or contact lenses (default test).

BCVA will be measured at baseline and at each following visit.

9.2.2 Laser Flare Photometry

Anterior Chamber Flare Assessment and Measurement Kowa LFM 600 and 700

The role of intra-ocular inflammation in driving disruption of blood-aqueous barrier and leading to the spreading of proteins and inflammatory cells into the aqueous humor has been previously established. The Standardization of Uveitis Nomenclature (SUV) system to evaluate and grade this kind of inflammatory leakage (flare) in the anterior chamber (AC) of the eye, ranging from 0 to 4+, is not useful or unreliable to detect and quantify AC

inflammation because the SUV test depends on the subjectivity of the evaluation and on the nonlinear grading of flare at the slit-lamp.

Currently, the only available system to quantitatively and objectively measure (with reproducibility) intra-ocular inflammation is the Kowa Laser Flare Meter (LFM) instrument. Such instrument includes a photomultiplier that amplifies the intensity of the light scattered by small molecules (flare) or larger particles (inflammatory cells) in the aqueous humor. The information is then processed by a computer and the result is expressed in photon counts per millisecond (ph/ms).

LFM instruments quantify back-scattered light both from small molecules and from larger particles such as inflammatory cells. Therefore, LFM measurements may be unreliable in eyes with extensive posterior synechiae or mature cataract due to increased background scattering of light. Seven measurements shall be obtained with LFM. The highest and the lowest LFM values are discarded and the mean and standard deviation of the remaining five LFM readings are automatically calculated. Patients do not experience any pain or discomfort during measurements. Aqueous flare intensity in the range of 2.9–3.9 ph/ms corresponds to healthy individuals between 20 and 40 years of age and they increase slightly with age, reaching 5.0–6.5 ph/ms for patients between 70 and 80 years of age.

Effective management of uveitis requires a reproducible and quantitative method to determine and monitor intraocular inflammation. Clinically meaningful changes in flare counts can be detected both in low and high-flare values because LFM allows measuring flare values that range between 3 and 1000 ph/ms on a linear scale. Gonzales *et al.* reported an inverse relationship between LFM flare and visual acuity in patients with uveitis. While no relationship was found between complications and anterior chamber cell or flare scores at the slit-lamp, a strong relationship was found between LFM flare and complications such as posterior synechia and macular edema.Intra-ocular inflammation evaluation by the Kowa Laser Flare Meter examination will be done at baseline and at each following visit.

9.2.3 **OCT**

Optical coherence tomography (OCT) Spectralis[®] (Heidelberg Egineering, Heidelberg Germany) is a non-invasive imaging test that uses light waves to take cross-section pictures of your retina, the light-sensitive tissue lining the back of the eye.

Cross-sectional visualization is an extremely powerful tool in the identification and assessment of retina abnormalities. The high resolving power ($10\mu m$ - Time Domain, $5\mu m$ – Spectral Domain) provides excellent detail for evaluating the vitreo-retinal interface, neurosensory retinal morphology, and the RPE-choroid complex. The ability to perform volumetric and retinal thickness analysis also provides a quantitative and repeatable method to evaluate surgical and pharmacological interventions. Individual high resolution line scans are a simple way to identify overt as well as very subtle retinal interface pathologies, such as a persistently adherent posterior hyaloid, fine epiretinal membranes, and vitreomacular

traction. In a procedure that is easily tolerated by most patients, well-placed line scans can differentiate between pseudo holes, lamellar holes and full thickness macular holes with a high degree of confidence. Line scans can also confirm the presence of retinal edema from various causes. When combined with serial thickness map or volume analysis, these different data sets provide a detailed picture of disease progression or therapeutic response.

OCT Spectralis[®] examination will be done at baseline and at each following visit.

9.2.4 Slit lamp

Slit-lamp biomicrography encompasses a wide spectrum of challenging photographic techniques for imaging structures and diseases of the anterior segment. Most photographic slit-lamps are equipped with two lighting sources, variable flash intensity, changeable magnifications, and changeable angles of illumination. Patients present a wide variety of disease entities that have specific textures, colors, transparency, size and depth. The slit lamp is a binocular microscope that provides the examiner with a stereoscopic (i.e. three-dimensional) view of the eye. The slit lamp allows examining the eye with a beam or "slit" of light (versus diffuse light) whose height and width can be adjusted. The slit of light, when directed at an angle, accentuates the anatomic structures of the eye, allowing close inspection. The slit lamp provides greater magnification (10 to 25 times) and illumination than most handheld devices (i.e. the Wood's lamp), which is necessary to diagnose a number of traumatic and non-traumatic disorders.

Slit lamp examination will be done at baseline and at each following visit.

9.2.5 Goldmann tonometry

Tonometry is the procedure to determine the intraocular pressure (IOP), the fluid pressure inside the eye. IOP is an important test in the evaluation of patients at risk from glaucoma. [1] Most tonometers are calibrated to measure pressure in millimeters of mercury (mmHg). Goldmann tonometry is considered to be the gold standard and most widely accepted method IOP test. A special disinfected prism is mounted on the tonometer head and then placed against the cornea. The examiner then uses a cobalt blue filter to view two green semi circles. The force applied to the tonometer head is then adjusted using a dial connected to a variable tension spring until the inner edges of the green semicircles in the viewfinder meet. When an area of 3.06 mm (0.120 in) has been flattened, the opposing forces of corneal rigidity and the tear film are roughly approximate and cancel each other out allowing the pressure in the eye to be determined from the force applied.

Intraocular pressure will be evaluated at baseline and at each following visit.

10 EVALUATIONS BY VISIT

10.1 Visit 1 (t₀)

- 1. Review the study with the subject (subject's legal representative) and obtain written informed consent
- 2. Assign a unique screening number to the subject
- 3. Record subject's demographics data
- 4. Record subject's medical history, including a history of uveitis, diagnosis date and prior uveitis treatments and the number of relapses during the previous year
- 5. Record subject's concomitant medications
- 6. Perform a physical examination of the subject
- 7. Vital signs collection
- 8. Urine dipstick specific pregnancy test
- 9. Perform a rheumatologic evaluation of the subject
- 10. Perform subject's ophthalmic evaluation (BCVA, Slip lamp, OCT Spectralis[®], LFM, Goldman tonometry).
- 11. Evaluation of uveitis symptoms by VAS (ocular pain, blurry vision, floaters, photophobia)
- 12. Evaluation of the patient's attitude towards the study treatment, through the Quick Questionnaire
- 13. Evaluate inclusion/exclusion criteria adherence
- 14. Randomize subject and dispense study product
- 15. Initiate subject diary.

After about 3 months of treatment the study staff will contact the patient by phone to verify that the study product is correctly taken.

10.2 Visit 2 (t_1 , 6 Months \pm 10 days)

- 1. Perform subject's ophthalmic evaluation (BCVA, Slip lamp, OCT Spectralis[®], LFM, Goldman tonometry)
- 2. Evaluation of uveitis symptoms by VAS (ocular pain, blurry vision, floaters, photophobia)
- 3. Perform a physical examination of the subject
- 4. Vital signs collection
- 5. Urine dipstick specific pregnancy test

- 6. Record any Adverse Event
- 7. Review subject's diary for Adverse Events and for dosing compliance
- 8. Study product collection and accountability
- 9. New diary and study product delivery
- 10. Concomitant medications review
- 11. Evaluation of the patient's attitude towards the study treatment, through the Quick Questionnaire

10.3 Visit 3 -End of Study (t₂, 12 Months \pm 10 days)

- 1. Perform subject's ophthalmic evaluation (BCVA, Slip lamp, OCT Spectralis[®], LFM, Goldman tonometry)
- 2. Evaluation of uveitis symptoms by VAS (ocular pain, blurry vision, floaters, photophobia)
- 3. Perform a physical examination of the subject
- 4. Vital signs collection
- 5. Urine dipstick specific pregnancy test
- 6. Record any Adverse Event
- 7. Review subject's diary for Adverse Events and for dosing compliance
- 8. Study product collection and accountability
- 9. Concomitant medications review
- 10. Evaluation of the patient's attitude towards the study treatment, through the Quick Questionnaire

10.4 Additional Unscheduled Visits in Case of Relapse

Should a relapse occur, an unscheduled visit will be performed including a complete ophthalmic evaluation. The number of cells in the AC will be determined by slit lamp, too.

Topical or systemic treatment will be prescribed to the subject according to the severity of the relapse and according to the best medical judgement.

Two following visits will be scheduled 2 and 6 weeks thereafter. During these visits a complete ophthalmic evaluation will be done.

If the subject is prescribed a systemic treatment for the relapse, he/she will be withdrawn from the study, and treated according to the best medical judgement.

If only topical treatments are prescribed, the subject will be allowed to continue the study. Depending on the onset time of the relapse it could be necessary to delay Visit 2 or Visit 3 around 2 months after the topical treatment conclusion.

Should Visit 2 be delayed, the delay will be recovered by keeping the date of Visit 3 at 12 months.

Should Visit 3 be delayed, the delay will not be recovered.

10.5 Early Withdrawal Visit

In the case of early withdrawal from the study, activities planned at Visit 3 will be performed, as far as possible.

11 DISCONTINUATION AND REPLACEMENT OF SUBJECTS

11.1 Early Discontinuation of Study Drug

A subject may be discontinued from the study treatment at any time if either the subject, and/or the investigator, and/or Eye Pharma feels that it is not in the subject's best interest to continue the study treatment. The following is a list of possible reasons for study treatment discontinuation:

- Subject withdrawal of consent
- Subject is not compliant with study procedures
- Need for the subject to start a systemic anti-inflammatory, immunosuppressive, biologicals therapy for uveitis or for other pathologies
- Adverse event that indicated in the opinion of the investigator that it would be in the best interest of the subject to discontinue study treatment
- Pregnancy
- Protocol violation requiring discontinuation of study treatment
- Missed follow-up
- Eye Pharma requests early study termination

If a subject is withdrawn from treatment due to an adverse event, the subject will be followed and treated by the investigator until the abnormal parameter or symptom has resolved or stabilized.

All subjects who discontinue the study treatment should come in for an early discontinuation visit as soon as possible and then they should be encouraged to complete all remaining scheduled visits and procedures.

All subjects are free to withdraw from participation at any time, for any reason, specified or unspecified, and without prejudice.

Reasonable attempts will be made by the investigator to obtain a reason for subject's withdrawals. The reason for the subject's withdrawal from the study will be specified in the subject's source documents.

11.2 **Replacement of Subjects**

Only subjects dropping out the study because they are beginning systemic therapy with antiinflammatory, immunosuppressive, biologic drugs will be replaced.

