14 STATISTICAL METHODS AND CONSIDERATIONS

Prior to the analysis of the final study data, a detailed Statistical Analysis Plan (SAP) will be issued, describing all analyses that will be performed. The SAP will contain any

modifications to the analysis plan described below. SAS 9.4 for windows (SAS Institute Inc., Cary, NC, USA) will be used for statistical analysis. A level of statistical significance (alpha) of 5% will be used to evaluate statistically significant differences between the two treatment groups, placebo and active treatment.

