14.3 Analysis of Primary Endpoint

The number and intensity of relapses will be assessed through instrumental analysis and physical examination. These endpoints will be assessed from baseline to end of treatment.

Mean and standard deviation will be used to describe the number of relapses per patient. The mean number of relapses per patient will be compared between the treatment groups using Student's t-test. ANOVA will be used to include predictive/confounding variables in the model.

In addition, a generalized linear mixed model (GLMM) with Poisson statistical distribution and with the number of relapses as dependent variable will be used to assess the effects of the treatment on reducing the number of relapses, also including in the model other potentially predicting/confounding variables.

The intensity of relapses will be scored as mild (either trace to 1+ cell OR flare \leq 20), moderate (2+ to 3+ cell OR Flare > 20 and < 100) and severe (4+ cell OR Hypopyon OR flare \geq 100). For each patient, the average intensity will be estimated as the mean of the intensity observed during each relapse. The average and the maximum intensity will be compared between treatment groups using Student's t-test. ANOVA will be used to include predictive/confounding variables in the model.

The mean number of relapses per patient observed during the study will be compared to the mean number of relapses reported the previous year within each treatment group using paired t-test or ANOVA, to eventually adjust for predictive/confounding variables. As group means can be somewhat deceptive with small number of events, the patients will be classified based on the number of relapses before treatment and then on the number of relapses after treatment. The number of patients that change class before and after treatment (for example, from a high number of relapses to a low number) will be described and compared between treatment groups.

The primary efficacy endpoints will be analyzed in the following hierarchical order: first, "the mean number and intensity of relapses during the study between treatment groups" and then "the reduction of mean number of relapses between the year before treatment and the study period".

The level of cell damage and inflammation will be assessed through Laser Flare Meter. The difference between treatment groups will be compared using ANCOVA, with the baseline level included in the model.

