14.7 Sample Size

In a previous study²⁵, 275 relapses on 106 patients were observed, corresponding to a mean number of relapses per patient of 2.6 (Standard deviation, SD: 0.7) while in the post-treatment group 36 relapses were registered corresponding to a mean number of relapses per patient of 0.34 relapses/patient. With a statistical power of 80% and a significance level (alpha) of 5% and a common SD of 0.7, 46 patients are needed to observe a difference of 0.6 relapses/patients between the two treatment groups (i.e., 2 relapses/patient in the NORFLO[®] ORO treatment group vs. 2.6 in the placebo treatment group). To take into account a potential dropout rate of 20% over 12 months, 60 patients will be recruited. Subjects dropping out the study because they are beginning systemic therapy with anti-inflammatory, immunosuppressive, biologic drugs will be replaced.

A second primary endpoint, i.e. the reduction of mean number of relapses between the year before treatment and the study period, will be examined. No formal sample size estimate is feasible on this endpoint, as it was not tested previously and no reasonable scenario can be drawn.

As the two endpoints will be assessed in a hierarchical order (first, "the mean number and intensity of relapses during the study between treatment groups" and then "the reduction of mean number of relapses between the year before treatment and the study period"), according to the "Points to consider on multiplicity issues in clinical trials", issued by the Committee for Proprietary Medicinal Products (CPMP - 2002), no sample size adjustment for multiplicity is needed.

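### Replacing only patients who leave to start systemic therapy conflicts with the 60-patient limit, and the plan does not say how replaced and replacement patients are analysed

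*Protocol*

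**What the plan says.** **Replacement.** Protocol 11.2: "Only subjects dropping out the study because they are beginning systemic therapy with antiinflammatory, immunosuppressive, biologic drugs will be replaced". Protocol 14.7 has the same rule, directly after the dropout allowance.

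**Trigger.** Protocol 10.4 withdraws a patient who is prescribed systemic treatment for a relapse. Protocol 7.1 drops a patient whose laser flare value exceeds 100 ph/ms. Protocol 14.3 grades a relapse as severe at a flare of 100 or more, and Protocol 5.1 makes the number and intensity of relapses the primary endpoint. Protocol 11.1 also lists systemic therapy for conditions other than uveitis as a reason for stopping.

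**Numbers.** Protocol 8.1: "Up to 60 eligible patients will be randomly assigned". Protocol 4.1 fixes 30 per arm. Protocol 14.7: "To take into account a potential dropout rate of 20% over 12 months, 60 patients will be recruited". The synopsis gives 3 months of enrolment and about 15 months in total.

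**Analysis.** Protocol 14.3: "The mean number of relapses per patient will be compared between the treatment groups using Student's t-test". A Poisson mixed model is added in Protocol 14.3 and SAP 11.4.1, with no mention of follow-up time. SAP 7 repeats 46, 60 and 20% but not the replacement rule, and SAP 13 does not list its omission as a deviation. The ITT definition (Protocol 14.1, SAP 8.1 and 11.1) makes no exception for replaced patients.

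**The concern.** Replacement that depends on the outcome needs a clear analysis rule, and there is none here. Two questions are open.

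- **How many are randomised?** Once 60 have been randomised, a single replacement makes 61, unless the replaced patient stops counting. Nothing says whether the patient does, or how a replacement is allocated.
- **Who is compared?** If replaced patients stopped counting, patients would be excluded according to their outcome. If they are kept, their relapse counts end at withdrawal, and a t-test on raw counts treats a shortened year as a full one. More withdrawals are expected in the arm with more relapses, so at equal per-relapse risk either route shrinks the difference.

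Timing adds to the conflict. Replacement can be triggered at any point in 12 months of treatment. A patient enrolled at month 3 who leaves at the end of treatment would be replaced at about month 15, and the replacement would finish at 3 + 12 + 12 = 27 months.

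**Working it through.** **1. The plan's own figures reproduce.** Inputs from Protocol 14.7 are "a common SD of 0.7, 46 patients are needed to observe" "a difference of 0.6 relapses/patients between the two treatment groups", with 80% power and alpha 5% (sidedness not stated; two-sided taken).

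- Normal approximation: 2 × (1.960 + 0.842)² × (0.7/0.6)² = 21.4, so 22 per arm, 44 in total.
- Exact two-sample t-test: 22.37, so 23 per arm, **46** in total (power 81.1%).
- Dropout: 46/0.80 = 57.5, so 58, close to the stated **60**.
- Without replacement, 60 × 0.80 = 48 completers (24 per arm, power 82.8%), so the allowance alone covers the 46.

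**2. Number randomised under replacement.** Let x be the share leaving for systemic therapy. The documents do not give it; 5% to 20% is assumed. If 60 places must be filled by patients who do not leave this way, the expected total is 60/(1 − x). If the 20% already includes these patients, the places needed are 46(1 − x)/0.80.

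| x | Randomised to fill 60 places | Places needed if the 20% includes x |
|---|---|---|
| 5% | 63 | 55 |
| 10% | 67 | 52 |
| 15% | 71 | 49 |
| 20% | 75 | 46 |

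Every total in the second column exceeds 60. The last column shows the possible overlap with the allowance: if the 20% covers only other dropouts, 58 stands and nothing overlaps.

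**3. Effect on the relapse comparison.** Assume Poisson relapses at r = 2.6 (placebo) and 2.0 (active) per year, the means in Protocol 14.7. Assume a probability p, equal in both arms, that a relapse leads to systemic therapy and withdrawal. All patients are in the analysis.

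- Share withdrawn: 1 − exp(−rp).
- Mean count if withdrawn patients are excluded: r(1 − p).
- Mean count if they are kept with counts ending at withdrawal: (1 − exp(−rp))/p.

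| p | Withdrawn, placebo / active | Difference if excluded | Difference if kept, truncated |
|---|---|---|---|
| 5% | 12.2% / 9.5% | 0.57 | 2.438 − 1.903 = 0.535 |
| 10% | 22.9% / 18.1% | 0.54 | 2.289 − 1.813 = 0.48 |
| 20% | 40.5% / 33.0% | 0.48 | 2.027 − 1.648 = 0.38 |

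The true difference is 0.60. Simulation gave 0.537, 0.476 and 0.375 for the last column. The p = 20% row implies more withdrawal than the 5% to 20% used in step 2.

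**4. Unequal risk.** With no true difference (2.6 in both arms) and p = 10% on placebo and 5% on active, excluding gives 2.34 − 2.47 = −0.13, and keeping truncated counts gives 2.289 − 2.438 = −0.15. Both are spurious differences against the active product.

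**5. Effect of counting follow-up time.** Under the same model, mean follow-up is the mean count divided by r. At p = 20% that is 2.027/2.6 = 0.780 years on placebo and 1.648/2.0 = 0.824 on active. Relapses divided by follow-up then return 2.6 and 2.0, provided the relapse that led to withdrawal is counted.

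**The case against.** Four stronger readings are tempting, and the documents do not support them.

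- **The dropout allowance is counted twice.** Protocol 14.7 uses the same dropout wording for both groups, so a reader might infer this. It does not say that the 20% includes patients who are replaced. Any double allowance would add patients and would not cost power.
- **Only the worst relapses trigger replacement.** Protocol 11.2 does not limit the reason for systemic therapy, 11.1 includes other conditions, and 10.4 leaves the choice to medical judgement.
- **Severe events disappear from the analysis.** The ITT definition retains a replaced patient who has post-randomisation data. SAP 11.4.1 takes intensity and flare from the first unscheduled visit, before cortisone, and Protocol 10.5 and 11.1 provide for a withdrawal visit. On this reading the severe relapse is captured.
- **The number randomised would reach 95 or more.** That follows at p = 20%, but only with unlimited chains of replacements, each followed for 12 months, which the stated timetable does not allow. The evidence on p points both ways. Protocol 2 cites a mean initial flare of 160 ph/ms in 44 HLA-B27 patients, and also reports that 8% of patients in the sponsor's earlier study worsened and needed other treatments. Neither figure is the share needing systemic therapy.

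Two further objections have force. If everyone is analysed as randomised, replacement itself does not bias the comparison; the dilution comes from withdrawal and truncated counts, so deleting the rule would not remove it. Also, the SAP describes recruitment in the past tense, so a change to the recruitment rule may come too late, and SAP 7 may omit the rule only because it is abridged. The analysis wording is still missing either way.

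**Conclusion.** The point stands in limited form. The replacement rule and the limits on number and timing cannot all hold, and the analysis of replaced and replacement patients is not stated. The sample size of 46 raised to 60 is not in error.

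The excess is about 3 to 15 patients above 60 if 5% to 20% leave for systemic therapy. The larger issue is the comparison itself. With patients kept under the ITT definition and follow-up ignored, a difference of 0.60 becomes about 0.54, 0.48 or 0.38 at 5%, 10% or 20% per-relapse risk. These sizes rest on Poisson relapses at the planning means, equal risk in both arms, counts that stop at withdrawal, and an assumed p. Unequal risk could push the result in another direction. This should be corrected before the analysis, but it does not invalidate the design.

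**What to change.** 1. **Reconcile the numbers** in Protocol 4.1, 8.1, 11.2 and 14.7, the synopsis and SAP 7. Either delete replacement from 11.2 and 14.7, or keep it and state the maximum number randomised, how a replacement is allocated, how late replacements fit the timetable, and what the 20% covers.
2. **State the analysis rule in the SAP.** Every randomised patient, replaced or replacement, is analysed in the assigned arm with all relapses counted, including the one that led to withdrawal. SAP 5.1, which limits the primary analysis to patients with relapses, must be brought into line with this.
3. **Count follow-up time.** Add log follow-up time as an offset in the Poisson model already planned. Use that model as the main comparison of relapse counts, or report it alongside the t-test.
4. **Record the change** in SAP 13. If recruitment is complete, report how many patients were replaced in each arm.

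None of this alters the clinical rules for systemic therapy or withdrawal. The cost is wording and a little more analysis work. If replacement is deleted, fewer patients complete 12 months: completers fall below 46 once more than 14 of 60 (23.3%) leave for any reason.
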